Factors Affecting Mortality in Critical Patients Admitted to Intensive Care Unit Due to Coronavirus Disease 2019

NCT number: NCT04659876

Date: 11.09.2020

Study Design, Population, and Data

Critical patients hospitalized due to COVID-19 in ICU of the University of Health Sciences Turkey, Diyarbakır Gazi Yaşargil Training and Research of Hospital between March 22 and September 1, 2020, were included in this study. The study was approved by the Ethics Committee of University of Health Sciences Turkey, Diyarbakır Gazi Yaşargil Training and Research of Hospital (No: 550, 11.09.2020). The trial was registered with clinicaltrials.gov (NCT04659876). This retrospective cohort study was conducted in accordance with the 2008 Declaration of Helsinki criteria.

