Patients were divided into two groups—those who survived (Survivors) and those who died (Non-survivors) during ICU follow-up. Both groups were compared in terms of clinical characteristics; APACHE II and SOFA scores and KDIGO stage; and laboratory values at the first admission to ICU. We attempted to determine the factors that affect mortality in critically ill patients hospitalized in ICU with COVID-19 diagnosis.

Statistical Analysis

SPSS 16.0 software for Windows (SPSS Inc., Chicago, IL, USA) was used for statistical analysis. Continuous data were expressed as means (SD or minimum–maximum), and categorical data were expressed as frequencies with percentages. Comparison of categorical data in the groups was performed using chi-square and Fisher's exact test, and the results were presented as n%. Kolmogorov–Smirnov test was used to determine whether the numerical data fit the normality distribution. Data conforming to the normality distribution were evaluated using Student t-test, and Mann–Whitney U and Kruskal–Wallis tests were employed to compare data that did not fit the normality distribution. Binary logistic regression was performed for the risk factors that were found to be significant in the univariate analysis. Odds ratio (OR) with 95% confidence interval (CI) was used to report the association between mortality and exposure to the risk factors. In all comparisons, P value of <0.05 was considered significant.

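### Naming Welch's t-test instead of Student's would protect the survivor versus non-survivor comparisons of means if group sizes and spreads both differ; a minor, optional improvement

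*Combined protocol and SAP*

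**What the plan says.** The study is a retrospective cohort of critical COVID-19 patients in one ICU. The Study Design, Population, and Data section divides them into "those who survived (Survivors) and those who died (Non-survivors) during ICU follow-up" and compares admission scores, KDIGO stage and laboratory values between the two groups.

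The Statistical Analysis section sets the route for numerical variables:

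- **Check:** "Kolmogorov–Smirnov test was used to determine whether the numerical data fit the normality distribution".
- **If the variable passes:** "Data conforming to the normality distribution were evaluated using Student t-test".
- **If it fails:** a rank test is used.
- **Threshold:** "In all comparisons, P value of <0.05 was considered significant".
- **Use of the result:** "Binary logistic regression was performed for the risk factors that were found to be significant in the univariate analysis".

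No check of equal variances, no unequal-variance form of the t-test and no rule for unequal spread appears anywhere. The software is named, but the form of the t-test to be reported is not.

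**The concern.** Student's t-test estimates one common variance from both groups. When the true variances differ, the larger group dominates that estimate. If the smaller group is the more variable one, the standard error is too small and the test rejects too often. If the larger group is the more variable one, the standard error is too large and the test rejects too seldom.

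Both ingredients are uncontrolled here, because the groups are formed by outcome. Nothing in the design makes them equal in size, and a variable related to death may differ in spread as well as in mean. The direction can also change from one variable to the next, so a reader could not treat all the p-values as cautious or all as generous.

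At stake is the p-value for a mean difference in those variables. Because the same threshold decides which factors enter the logistic model, an error can carry into that selection. The clearest loss is a real mean difference that is missed when the larger group is the more variable.

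**Working it through.** **Inputs from the document.** The nominal level is 0.05 for every comparison. The sides are not stated, and two-sided is assumed. There is no sample size, death count or SD, so the plan has no figure to reproduce.

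**Assumed inputs.** Group splits of 100/50, 70/30 and 75/25, SD ratios of 1.2, 1.5 and 2 in either direction, and normal data.

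**Formula.** With group sizes n1, n2 and true SDs s1, s2:

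- pooled variance: sp² = [(n1−1)s1² + (n2−1)s2²] / (n1+n2−2)
- r = √{ sp²(1/n1 + 1/n2) / (s1²/n1 + s2²/n2) }, the standard error that Student's test uses divided by the true one
- large-sample size of Student's test: 2[1 − Φ(1.96 r)]

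**Two cases where the problem vanishes.** If s1 = s2, then r = 1 for any split. If n1 = n2, then r = 1 for any SDs. Both inequalities are needed.

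**Example 1: 30 versus 70, smaller group with 1.5 times the SD.**

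- sp² = (29×2.25 + 69×1)/98 = 134.25/98 = 1.370
- variance used: 1.370 × (1/30 + 1/70) = 0.0652
- true variance: 2.25/30 + 1/70 = 0.0893
- r = √(0.0652/0.0893) = 0.855
- size = 2[1 − Φ(1.675)] = 9.4%

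**Example 2: the same split, larger group with 1.5 times the SD.**

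- sp² = (29×1 + 69×2.25)/98 = 184.25/98 = 1.880
- variance used: 1.880 × (1/30 + 1/70) = 0.0895
- true variance: 1/30 + 2.25/70 = 0.0655
- r = 1.169
- size = 2[1 − Φ(2.292)] = 2.2%

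**Size of Student's test over the assumed range** (formula; in brackets, simulation with 40,000 data sets per setting, where available):

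| Split | SD ratio | Smaller group more variable | Larger group more variable |
|---|---|---|---|
| 100/50 | 1.2 | 6.5% | 3.7% |
| 100/50 | 1.5 | 8.5% (8.5%) | 2.6% (2.4%) |
| 100/50 | 2 | 11.0% (11.1%) | 1.6% (1.7%) |
| 70/30 | 1.2 | 6.8% | 3.5% |
| 70/30 | 1.5 | 9.4% (9.6%) | 2.2% (2.2%) |
| 70/30 | 2 | 12.6% (12.5%) | 1.2% (1.3%) |
| 75/25 | 1.2 | 7.4% | 3.2% |
| 75/25 | 1.5 | 10.8% (10.5%) | 1.7% (1.7%) |
| 75/25 | 2 | 15.2% (15.3%) | 0.7% (0.8%) |

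In the same simulations Welch's test stayed between 4.7% and 5.2%.

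**Power lost in the conservative direction.** Take Example 2 with a true difference of 0.6 of the smaller group's SD.

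- The true standard error is √0.0655 = 0.256, so the standardised difference is 0.6/0.256 = 2.345.
- Welch: Φ(2.345 − 1.96) = 65%.
- Student: the effective cut-off is 1.96 × 1.169 = 2.292, so power is Φ(2.345 − 2.292) = 52%.
- Simulation, which uses t rather than normal quantiles, gives about 64% and 52%.

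**Cost of Welch when variances are equal** (simulated). The power loss is about 0.2 points at 100/50, 0.5 at 70/30 and 1.2 at 75/25.

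**The case against.** The strongest objection concerns false positives. A reader might infer that Student's test lets factors with no relation to death into the logistic model. The documents do not support that. The groups are the outcome, so a factor independent of death has one and the same distribution in both, including the same SD. Then r = 1, and simulation puts the size of Student's test at 4.8% to 5.2%. The inflated figures need equal means with unequal SDs. Such a factor is associated with death: for normal data the log-odds of death is then quadratic in the factor. Its rejection is an error about the mean difference only. This objection stands, and it limits the harm as stated in the verdict.

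A reader might also infer that published confidence intervals are wrong. The plan promises intervals only for odds ratios, which the t-test does not produce.

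Other points on that side:

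- **The sizes and SD ratios are assumptions.** This stands. At a ratio of 1.2 the distortion is mild.
- **The normality check filters extreme cases.** This stands in part. The plan does not say whether the check is applied to the pooled data or by group. If pooled, a threefold SD ratio in the smaller group would fail a Lilliefors-corrected check about 93% of the time at 100/50 and 83% at 70/30, so such ratios are not relied on here. Ratios of 1.5 mostly pass.
- **The term Student t-test is sometimes used loosely for either form.** This is possible. If the unequal-variance form was used, the text should say so.
- **The t-test is a screen, and the main result is the odds ratio.** This is true, but the screen decides which factors get an adjusted odds ratio.

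**Conclusion.** The point holds as a cheap improvement and not as a demonstrated error. As written, the plan uses a pooled-variance test for groups whose sizes and spreads it does not control, and it checks only normality. If both sizes and SDs differ, the p-value for the mean difference is off. For the assumed splits (100/50 to 75/25) and SD ratios (1.2 to 2), the true size is about 6% to 15% in one direction and about 4% to 1% in the other. In the conservative direction real mean differences can be missed, and those factors would then fail the entry screen for the logistic model.

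The effect is confined to variables that pass the normality check and whose spread differs by vital status. Whether any variable in this cohort meets those conditions cannot be told from the documents, so no reported result can be called wrong on this ground. Severity is minor, and the change is optional.

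**What to change.** In the Statistical Analysis section, replace Student t-test with Welch's unequal-variance t-test for all survivor versus non-survivor comparisons of means. Do not add a preliminary test of equal variances: Welch's test holds its level whether or not the variances are equal, so a pre-test is not needed. If the unequal-variance form was already used, a one-line statement to that effect is enough.

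The cost is one edited phrase and, where Student's form was used, a re-run of those comparisons and of the screen that follows. No new data are needed. The statistical price is the small power loss at equal variances shown above: half a point or less at 100/50 and 70/30, and a little over 1 point at 75/25.

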Critical patients diagnosed with COVID-19 on the dates specified, followed up in ICU, aged >18 years, in serious need of oxygen support according to WHO and the temporary guidelines of T.C. Science Board of the Ministry of Health [presence of fever, muscle/joint pain, cough, and sore throat; tachypnea (30 breaths/min) or dyspnea; use of extra respiratory muscles; SpO₂ level below of ≤90% in room air; bilateral diffuse pneumonia symptom detected on chest radiography or computerized tomography (CT); and PaO₂/ FiO₂ ratio of <300], and developed or had complications including severe pneumonia, ARDS, sepsis/septic shock, and acute renal failure were included in the study. Patients with COVID-19 aged <18 years with mild-to-moderate symptoms, no respiratory distress, and no signs of diffuse pneumonia on chest X-ray or CT as well as ICU patients excepted from COVID-19 diagnosis were excluded from the study. In addition, patients whose complete data could not be accessed from the hospital system or the patient file records were excluded. When the patients were admitted to ICU for the first time, their clinical conditions were evaluated with APACHE II and SOFA scores, and the degree of renal failure was evaluated using the Kidney Disease: Improving Global Outcomes (KDIGO) classification. Age; sex; comorbidity; ABO and Rh blood groups; APACHE II and SOFA scores and KDIGO stage during admission to ICU; hemogram parameters [white blood cell (WBC), neutrophil, lymphocyte, neutrophil/lymphocyte (N/L) ratio, hemoglobin, hematocrit, and platelet count]; blood gas values [pH, partial oxygen pressure (PO₂), partial carbon dioxide pressure (PCO₂), bicarbonate (HCO₃), and lactate]; coagulation parameters [prothrombin time (PTZ) and D-dimer]; blood biochemistry results [creatinine kinase (CK), lactate dehydrogenase (LDH), C-

reactive protein (CRP), urea, creatinine, alanine aminotransferase (ALT), aspartate aminotransferase (AST), total bilirubin, direct bilirubin, and indirect bilirubin]; and procalcitonin (PCT) and ferritin levels of the patients were recorded. Moreover, the length of stay in ICU and whether the patient died or survived were recorded. Patient data were rechecked for erroneous information before the last data entry and entered into a computerized database.

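### The regression can adjust age and comorbidity for admission severity that is partly their consequence, so their ORs show only the association that severity does not explain

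*Combined protocol and SAP*

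**What the plan says.** The aim, in the combined protocol and SAP under Study Design, Population, and Data, is worded causally: "We attempted to determine the factors that affect mortality in critically ill patients hospitalized in ICU with COVID-19 diagnosis". The title uses similar wording. No prediction-only aim is stated.

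The same section puts host factors and admission severity in one list of recorded variables: "Age; sex; comorbidity; ABO and Rh blood groups; APACHE II and SOFA scores and KDIGO stage during admission to ICU", followed by the laboratory values. The severity scores are dated: "When the patients were admitted to ICU for the first time, their clinical conditions were evaluated with APACHE II and SOFA scores". The outcome groups are "those who survived (Survivors) and those who died (Non-survivors) during ICU follow-up".

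The crude comparison, made on values at entry to intensive care, covers all of these variables: "Both groups were compared in terms of clinical characteristics; APACHE II and SOFA scores and KDIGO stage; and laboratory values at the first admission to". The Statistical Analysis section then gives the entry rule, "Binary logistic regression was performed for the risk factors that were found to be significant in the univariate analysis", the effect measure, "Odds ratio (OR) with 95% confidence interval (CI) was used to report the association between mortality and exposure to the risk factors", and the threshold, "In all comparisons, P value of <0.05 was considered significant".

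The plan gives no order between the factors, no blocks and no host-only model. It does not say that a host factor's adjusted OR means something different from a severity marker's.

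**The concern.** Age, sex, comorbidity and blood group are fixed before the patient reaches ICU. Organ dysfunction and laboratory values at ICU admission come later, and are plausibly in part the result of age and comorbidity. If a host factor and a severity measure both pass the screen and enter one model, the host factor's coefficient is its association with death at a fixed level of admission severity. Whatever acts through severity is removed.

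That is a legitimate quantity, but it does not answer whether the factor affects mortality. One table of ORs would answer different questions on different rows. An older patient's excess risk that runs through worse organ function at admission would appear as a weak or non-significant age OR, and could be read as no effect of age.

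This is a matter of time order, not of collinearity. Variance-inflation checks or a larger sample would not remove it.

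**Working it through.** **Figure to reproduce.** None. The documents state no sample size, event count, power or effect size. Every numerical input below is assumed; the documents supply only the structure (host factors first, severity at ICU admission next, death in ICU last).

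**Set-up.** Age A is in decades, SD 1.4. The severity score is S = kA + e, with SD(e) = 3. The log-odds of death are c + dA + bS, with mortality about 50%.

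- With S in the model, the age coefficient is d.
- Without S, it is approximately (d + kb) / sqrt(1 + 0.346 × (3b)²). Here 0.346 = (16√3 / 15π)², the usual logistic-normal approximation for averaging over e.

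**Example.** Take k = 1.0, d = 0.20, b = 0.25. The numerator is 0.20 + 1.0 × 0.25 = 0.45. The denominator is sqrt(1 + 0.346 × 0.5625) = 1.093. The ratio is 0.412, so the OR is exp(0.412) = 1.51 without the score, against exp(0.20) = 1.22 with it.

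Simulation used 400,000 patients for the ORs, and 800 samples of N = 150 for the share with P<0.05 for age:

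| k | d | b | OR without S, formula | OR without S, simulated | OR with S, simulated | P<0.05 without S | P<0.05 with S |
|---|---|---|---|---|---|---|---|
| 1.0 | 0.20 | 0.25 | 1.51 | 1.49 | 1.22 | 91% | 32% |
| 0.7 | 0.20 | 0.25 | 1.41 | 1.39 | 1.22 | 76% | 27% |
| 1.0 | 0.20 | 0.20 | 1.46 | 1.45 | 1.23 | 87% | 31% |
| 0.5 | 0.20 | 0.20 | 1.33 | 1.32 | 1.22 | 65% | 35% |
| 1.0 | 0 | 0.25 | 1.26 | 1.26 | 1.01 | – | – |

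Repeat runs agreed within simulation error. Among samples with d = 0.20 in which age passed the crude screen, roughly 45-67% had a non-significant age term in the joint model.

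**Not collinearity.** The age-score correlation is 1.4k / sqrt((1.4k)² + 9). This is 0.23 at k = 0.5 and 0.42 at k = 1.0. The largest variance inflation is 1 / (1 − 1.96/10.96) = 1.22.

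**Second set-up.** A binary host factor (50% prevalence) shifts severity by a SD, and severity has log-OR 1.0 per SD.

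- a = 0.5, direct OR 1.35: host OR 1.96 without severity, 1.37 with it.
- a = 0.5, no direct effect: 1.51 without, 1.00 with.
- a = 0, direct OR 1.65: 1.51 without, 1.64 with. Nothing is lost; the small rise is non-collapsibility of the OR.

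After the crude screen, significance was lost in the joint model in 62-75% of samples (a = 0.5, direct log-OR 0.3; n from 150 to 600). In a control with no path through severity (a = 0, direct log-OR 0.8) it was lost in 0-6%. At n = 150 these two cases passed the screen about equally often (50% and 48%), so the screen itself does not produce the loss.

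**Unmeasured common cause of severity and death.** With a true direct OR of 1.00, the joint-model OR was 0.88. The severity-adjusted OR is therefore not safely a direct effect either.

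**Does a host-only model recover the age effect?** Not if it contains comorbidity, which may itself follow from age. Assumed inputs: comorbidity log-odds rise 0.3-0.5 per decade; comorbidity has direct log-OR 0.7-1.0 and adds 2 score points; age adds 0.7 point per decade; 0.2 log-odds per point; direct age 0.2. The age OR per decade was about 1.44-1.55 alone, 1.37-1.38 beside comorbidity, and 1.22 once the score was added.

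**The case against.** The strongest reply is that nothing is hidden. A factor reaches the regression only after a significant crude comparison, so any host factor that weakens there has already been shown to be associated with death. This stands, and it limits the harm. A reader might infer that the plan will report real factors as having no effect. The documents do not support that: they contain no rule for interpreting a factor that loses significance, and the crude comparison is planned. What remains missing is an effect size for host factors adjusted only for other host factors, and a label for the ORs that are reported.

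A reader might also take one joint model as stated. It is not; no entry method is given, although joint entry is the natural reading. The mixing also requires a host factor and a severity measure both to pass the screen. Nothing in the plan prevents this.

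A severity-adjusted association is a proper quantity for prognosis at admission, and the plan never names a total effect as its target. But the stated aim is factors that affect mortality, and the plan does not tell the reader which rows of the table answer it.

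The path from host factor to severity is assumed. It is plausible for age and comorbidity and much less certain for sex and blood group.

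The size is also assumed. The 27-35% detection with the score mainly reflects the chosen direct OR of about 1.22 and N = 150. With no age-severity path, detection was 32% without the score and 33% with it. The simulations show the mechanism, not its size in this cohort.

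**Conclusion.** The point holds as a limitation of what the adjusted host-factor ORs mean. Following the plan can yield ORs for age and comorbidity that leave out the part of their association running through admission severity, and a loss of significance there can be misread against the stated aim.

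For age, the OR per decade moves from about 1.3-1.5 to about 1.2 under the assumed inputs, or to about 1.0 if all of the effect runs through severity. None of these is an estimate for this study. The conclusion rests on three things: joint entry, both kinds of factor passing the screen, and a real path from host factor to severity.

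The cohort is also restricted to ICU patients with PaO₂/FiO₂ below 300 and serious complications, which already conditions on severity. No model on these data gives the effect of a host factor across all COVID-19 patients. The change is worth making because it is cheap and bears on the main result; the issue does not invalidate the analysis.

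**What to change.** On the same data, report two sets of results.

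1. **Host factors without admission severity or laboratory values.** Estimate age without adjustment for comorbidity, for example in a model with age and sex, and ABO/Rh if wanted. Estimate comorbidity adjusted for age and sex.
2. **A second model adding admission severity and laboratory factors.** Use it for the prognostic value of those factors given the host factors.

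State in the Statistical Analysis section which model each OR is read from, and whether the screened factors enter jointly. Label host-factor ORs in the second model as the association not explained by admission severity. Do not treat loss of significance there as evidence of no effect. State that all ORs are associations among patients already admitted to ICU.

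The cost is one or two extra logistic models, a slightly longer results table and a few sentences of text. No new data or patients are needed.
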